6.2.3 Clinical/Medication History

The investigator should review the subject's clinical history, including details relating to DMD and any other medical conditions. Information regarding current medications must be captured on the concomitant medication CRF. Details regarding corticosteroid use within 12 months prior to study entry will be collected on a specific CRF.

6.2.4 Hepatitis Screen

Tests include hepatitis A antibody, hepatitis B core antibody, and hepatitis C antibody. The Central Laboratory Manual should be consulted for collection, processing, and shipping details. ***Note: Only hepatitis B and C results are required for eligibility determination.***

6.2.5 Vital Signs

Vital signs (including systolic and diastolic blood pressure, pulse rate, and body temperature) will be monitored at Screening (Visit 1), baseline (Visit 2), Week 12 (Visit 3) Week 24 (Visit 4), Week 36 (Visit 5), Week 48 (Visit 6), Week 60 (Visit 7), Week 72 (Visit 8), Week 96 (Visit 9), Week 120 (Visit 10), and Week 144 (Visit 11 - End of Treatment/Premature Discontinuation). The pulse rate and blood pressure determinations will be performed with the subject in a sitting position after a 5-minute rest. Blood pressure will be measured in triplicate and the average will be recorded, as described in the study reference manual.

6.2.6 Height, Weight, and Physical Examination

Height (in cm) and weight (in kg) will be measured at Screening (Visit 1), Baseline (Visit 2), Week 12 (Visit 3), Week 24 (Visit 4), Week 36 (Visit 5), Week 48 (Visit 6), Week 60 (Visit 7), Week 72 (Visit 8), Week 96 (Visit 9), Week 120 (Visit 10), and Week 144 (Visit 11 - End of Treatment/Premature Discontinuation). If the subject is unable to stand, sitting arm span and ulna length should be assessed as surrogate measurements for height.

A full physical examination (including evaluation of cardiovascular system, chest and lungs, thyroid, abdomen, nervous system, skin and mucosae, musculoskeletal system, eyes, ears, nose, mouth, throat, spine, lymph nodes, extremities, and genitourinary) will be conducted at Screening (Visit 1), Week 72 (Visit 8), and Week 144 (Visit 11 - End of Treatment/Premature Discontinuation).

A symptom-directed physical examination will be conducted at Baseline (Visit 2), Week 24 (Visit 4), and Week 48 (Visit 6).

Physical examinations may also be performed at any time during the study as clinically indicated.

6.2.7 Genotyping

Blood for genotyping of genetic modifier candidates (latent TGF-beta binding protein 4 [LTBP4], secreted phosphoprotein 1 [SPP1], cluster of differentiation 40 [CD40]) and thrombospondin 1 [TBHS1] will be collected at Baseline (Visit 2). Sequencing of the dystrophin gene to confirm the presence of a nonsense mutation also will be performed. This sample will be stored at the central laboratory. This blood sample will be destroyed after the

test is completed and a final report is generated by the designated central laboratory. The Study Manual should be consulted for collection, processing, and shipping details.

6.2.8 Hematology Laboratory Assessment

Hematology laboratory assessments will include white blood cell count with differential, hemoglobin, hematocrit, mean corpuscular volume, mean corpuscular hemoglobin, mean corpuscular hemoglobin concentration, total red cell count with morphology, and platelet count. These parameters will be measured at Screening (Visit 1), baseline (Visit 2), Week 24 (Visit 4), Week 48 (Visit 6), Week 72 (Visit 8), Week 96 (Visit 9), Week 120 (Visit 10), and Week 144 (Visit 11 - End of Treatment/Premature Discontinuation). Hematology parameters will be analyzed by the central laboratory. The Central Laboratory Manual should be consulted for collection, processing, and shipping details.

6.2.9 Serum Biochemistry Laboratory Assessment

Biochemistry laboratory assessments will include sodium, potassium, chloride, bicarbonate, BUN, creatinine, magnesium, calcium, phosphorus, uric acid, glucose, total protein, albumin, globulin, albumin:globulin ratio, bilirubin (direct and indirect), AST, ALT, GGT, CK, lactate dehydrogenase (LDH), alkaline phosphatase, total cholesterol, high-density lipoprotein (HDL), low-density lipoprotein (LDL), triglycerides, and cystatin C. These parameters will be measured at Screening (Visit 1), Baseline (Visit 2), Week 24 (Visit 4), Week 48 (Visit 6), Week 72 (Visit 8), Week 96 (Visit 9), Week 120 (Visit 10), and Week 144 (Visit 11 - End of Treatment/Premature Discontinuation). Subjects should have fasted for at least 8 hours prior to blood collection; this is not necessary at screening (Visit 1). Biochemistry parameters will be analyzed by the central laboratory. The Central Laboratory Manual should be consulted for collection, processing, and shipping details.

6.2.10 Pharmacokinetic Assessment

Ataluren concentrations in PK samples will be determined using a validated LC-MS/MS method. The Central Laboratory Manual should be consulted for timing of collection, processing, and shipping details.

6.2.11 Urinalysis

Urinalysis will include analysis for pH, specific gravity, glucose, ketones, blood, protein, urobilinogen, bilirubin, nitrite, and leukocytes. These parameters will be measured at Screening (Visit 1), Baseline (Visit 2), Week 24 (Visit 4), Week 48 (Visit 6), Week 72 (Visit 8), Week 96 (Visit 9), Week 120 (Visit 10), and Week 144 (Visit 11 - End of Treatment/Premature Discontinuation). These parameters will be analyzed by the central laboratory. Urine samples will also be collected and shipped to central laboratory for assessment of urine protein, creatinine, osmolality, and urinalysis. The Central Laboratory Manual should be consulted for collection, processing, and shipping details.

6.2.12 12-Lead ECG

A 12-lead ECG will be obtained at Screening (Visit 1), Week 24 (Visit 4), Week 48 (Visit 6), Week 72 (Visit 8), and Week 144 (Visit 11 - End of Treatment/Premature Discontinuation). The ECG will be performed and interpreted locally. The findings will be captured in source documents and with the CRF.

A follow-up ECG may also be performed at any time during the study as clinically indicated at the discretion of the investigator. The PTC medical monitor must be informed via e-mail that an additional ECG was obtained and the SAE reporting process should be followed, if applicable.

6.2.13 Spirometry

Spirometric evaluation of FVC and other parameters (eg, maximal inspiratory and expiratory pressures, peak expiratory flow) in the sitting position will be performed at screening (Visit 1), Baseline (Visit 2), Week 72 (Visit 8), and Week 144 (Visit 11 - End of Treatment/Premature Discontinuation). If a patient loses ambulation as determined by inability to perform the 10-meter run/walk test within 30 seconds at a clinic visit, then spirometry will be performed at that visit and at all subsequent visits.

6.2.14 Echocardiogram

An echocardiogram will be obtained at Screening (Visit 1), Week 72 (Visit 8), and Week 144 (Visit 11 – End of Treatment/Premature Discontinuation).

6.2.15 Study Drug Randomization

After the completion of the 2nd baseline 6MWT at Week 1, Day 2 (Visit 2, Day 2), a site representative should access the IRT system, following investigator confirmation of eligibility and supply the necessary information to obtain a subject randomization number and treatment assignment (see Section 4.3) in anticipation of administration of the first dose of study drug on the morning or afternoon on Day 2 of the Baseline visit (Visit 2, Day 2). If there is a delay in starting of study drug administration, all subsequent visits will be timed relative to the date that dosing is initiated.

6.2.16 Study Drug Administration

Refer to Section 5.2.

6.2.17 Study Drug Compliance

Subjects and/or parents/caregivers will return unused study drug (sachets and kits) to the study site for full compliance assessments.

6.2.18 Adverse Events

AEs must be assessed and documented at each clinic visit. This information will be collected at Screening (Visit 1), Baseline (Visit 2), Week 12 (Visit 3) Week 24 (Visit 4), Week 36 (Visit 5), Week 48 (Visit 6), Week 60 (Visit 7), Week 72 (Visit 8), Week 96 (Visit 9), Week 120 (Visit 10), and Week 144 (Visit 11 - End of Treatment/Premature Discontinuation). AEs also will be assessed during the Post-Treatment Follow-Up Phone Call (4 weeks post discontinuation of study drug). In addition, subjects and patients/caregivers will be encouraged to report AEs of concern at any time in the intervals between visits.

6.2.19 Concomitant Medications

Information regarding any concomitant medications administered, as well as information regarding all non-drug therapies, will be collected throughout the study. This information will be collected at Screening (Visit 1), Baseline (Visit 2), Week 12 (Visit 3) Week 24 (Visit 4), Week 36 (Visit 5), Week 48 (Visit 6), Week 60 (Visit 7), Week 72 (Visit 8), Week 96 (Visit 9), Week 120 (Visit 10), and Week 144 (Visit 11 - End of Treatment/Premature Discontinuation). Concomitant medication information also will be collected during the Post-Treatment Follow-Up Phone Call (4 weeks post discontinuation of study drug).

6.2.20 Myometry

Myometry will be performed only in subjects who are <7 years old at baseline.

Upper and lower extremity myometry will be performed using a myometer following standardized procedures (see Study Manual for detailed instructions). Muscle groups to be evaluated include knee extensors and elbow flexors. Bilateral assessments should be done and 3 measurements should be recorded from each muscle group on each side if possible. These parameters will be monitored at screening (Visit 1), Baseline (Visit 2), Week 12 (Visit 3) Week 24 (Visit 4), Week 36 (Visit 5), Week 48 (Visit 6), Week 60 (Visit 7), Week 72 (Visit 8), Week 96 (Visit 9), Week 120 (Visit 10), and Week 144 (Visit 11 - End of Treatment/Premature Discontinuation).

6.2.21 Performance of Upper Limb

PUL will be assessed only in subjects who are ≥ 7 years old at baseline.

PUL will be administered using standardized equipment and procedures (see Study Manual for detailed instructions) at screening (Visit 1), Baseline (Visit 2), Week 12 (Visit 3) Week 24 (Visit 4), Week 36 (Visit 5), Week 48 (Visit 6), Week 60 (Visit 7), Week 72 (Visit 8), Week 96 (Visit 9), Week 120 (Visit 10), and Week 144 (Visit 11 - End of Treatment/Premature Discontinuation).

6.2.22 6-Minute Walk Test

Ambulation and endurance will be assessed via the 6MWT following standardized procedures (see Study Manual for detailed instructions). The 6MWT will be performed at Screening (Visit 1), Baseline (Visit 2, two 6MWTs performed), Week 12 (Visit 3) Week 24 (Visit 4), Week 36 (Visit 5), Week 48 (Visit 6), Week 60 (Visit 7), Week 72 (Visit 8, two 6MWTs performed), Week 96 (Visit 9), Week 120 (Visit 10), and Week 144 (Visit 11 - End of Treatment/Premature Discontinuation).

6.2.23 North Star Ambulatory Assessment

The NSAA will be used to evaluate physical function, using standardized procedures (see Study Manual for detailed instructions). The NSAA will be performed at Screening (Visit 1), Baseline (Visit 2), Week 12 (Visit 3) Week 24 (Visit 4), Week 36 (Visit 5), Week 48 (Visit 6), Week 60 (Visit 7), Week 72 (Visit 8), Week 96 (Visit 9), Week 120 (Visit 10), and Week 144 (Visit 11 - End of Treatment/Premature Discontinuation).

6.2.24 Timed Function Tests

Timed function tests of peak physical capacity, including the times taken to climb 4 stairs, and descend 4 stairs, will be performed using standardized procedures (see Study Manual for detailed instructions). These assessments will be performed at Screening (Visit 1), Baseline (Visit 2), Week 12 (Visit 3) Week 24 (Visit 4), Week 36 (Visit 5), Week 48 (Visit 6), Week 60 (Visit 7), Week 72 (Visit 8), Week 96 (Visit 9), Week 120 (Visit 10), and Week 144 (Visit 11 - End of Treatment/Premature Discontinuation).

Time to run/walk 10 meters and time to stand from supine will be assessed as part of the NSAA (Section [6.2.23](#)).

6.2.25 DMD Upper Limb PROM

DMD Upper Limb PROM will be assessed only in subjects who are ≥ 7 years old at baseline.

The DMD Upper Limb PROM questionnaire will be available in all languages relevant for this study and will be completed by the parent/caregiver. If possible, the same parent/caregiver should complete the questionnaire each time. The DMD Upper Limb PROM questionnaire will be completed at Baseline (Visit 2), Week 12 (Visit 3) Week 24 (Visit 4), Week 36 (Visit 5), Week 48 (Visit 6), Week 60 (Visit 7), Week 72 (Visit 8), Week 96 (Visit 9), Week 120 (Visit 10), Week 144 (Visit 11 - End of Treatment/Premature Discontinuation). Refer to the Study Manual for further details on how to administer the DMD Upper Limb PROM questionnaire.

6.2.26 Magnetic Resonance Imaging/Spectroscopy

MRI and/or magnetic resonance spectroscopy (MRS) will be conducted at a subset of sites that have been pre-qualified by a central imaging vendor to perform this assessment. To be pre-qualified, a site must have access to a whole-body scanner and appropriate personnel at the site must have been trained on the procedure for data acquisition. A list of qualified sites and documentation of equipment and training, as well as whether the site is performing MRI only or MRI and MRS, will be maintained. MRI/MRS data will be analyzed centrally. MRI/MRS will be performed at Baseline (Visit 2), Week 24 (Visit 4), Week 48 (Visit 6),

Week 72 (Visit 8), and Week 144 (Visit 11 – End of Treatment/Premature Discontinuation). The baseline imaging may be performed during the screening period, and post-baseline imaging may be performed ± 4 weeks of visit date. To the extent possible, excessive physical activity should be avoided for 3 days prior to imaging assessments.

Subjects with a contraindication to imaging (eg, subjects with a fear of closed spaces or with metal objects in the body that are not scanner-safe) should not undergo imaging but can participate in the rest of the study.

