5 STUDY DRUG ADMINISTRATION

5.1 Investigational Product

5.1.1 Ataluren (PTC124)

Blinded ataluren (treatment through Week 72) as well as open-label ataluren (treatment from Week 73 to Week 144) will be provided as white to off-white granules for oral suspension. The drug substance and drug product are manufactured under current good manufacturing practice (cGMP) conditions. The formulation includes matrix and suspending agents, surfactants, and various excipients that aid in the manufacturing process. The granules for oral suspension are packaged in aluminum foil, child-resistant sachets (packets) and supplied in dose strengths containing 125, 250, or 1000 mg of the active drug substance. For administration, the granules in the sachet may be mixed with water, fruit juice, fruit punch, or milk (skim, 1% fat, 2% fat, whole milk, chocolate milk, soy milk, or lactose-free milk), or semi-solid food (yogurt, pudding, or applesauce).

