5.2 Study Drug Treatment

5.2.1 Duration of Treatment

Treatment will comprise continuous daily administration of double-blind ataluren or placebo for 72 weeks followed by continuous daily administration of open-label ataluren for an additional 72 weeks.

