6 SCHEDULE OF EVENTS AND STUDY PARAMETERS

6.1 Schedule of Events

The proposed types and timing of data to be recorded are described in [Table 3](#) (double-blind treatment period) and [Table 4](#) (open-label treatment period). Refer to Section [6.2](#) for cross-referenced explanations of the study procedures described in the tables.

Table 3. Schedule of Events (Double-Blind Treatment Period)

Study Period	Screening	Double-Blind Treatment								Notes
Study Week	-2 weeks	1	12	24	36	48	60	72		2-week screening period may be extended by 1 week if necessary to schedule pretreatment MRI
Visit Window (days)			±7	±7	±7	±7	±7	±7		
Visit Number	1	2	3	4	5	6	7	8		At Visit 2, complete assessments before first dose
Visit Day		1 2						1 2		2-day visits only at Visit 2 and Visit 8
Informed consent	X									May be obtained prior to Visit 1 (eg, by phone)
Enter subject in IRT system	X									Access IRT system to enter subject
Clinical and medication history	X									
Hepatitis screen	X									
Urinalysis sample	X	X		X		X		X		
EQ-5D and DMDSAT	X	X		X	X	X	X	X	X	Provided to subject at Visit 1 for at-home completion between visits and reviewed for compliance in clinic
DMD Upper Limb PROM		X		X	X	X	X	X	X	Performed only in subjects ≥7 years at baseline
Height	X	X		X	X	X	X	X	X	
Weight	X	X		X	X	X	X	X	X	
Physical examination	X	X		X		X		X		Full (Visit 1, 8) or symptom-directed (Visit 2, 4, 6)
Concomitant medications	X	X		X	X	X	X	X	X	
Adverse events	X	X		X	X	X	X	X	X	
Genotyping sample		X								
Hematology sample	X	X		X		X		X		
Biochemistry sample	X	X		X		X		X		To be collected in fasted state (except Visit 1)
Vital signs	X	X		X	X	X	X	X	X	
Myometry	X	X		X	X	X	X	X	X	Performed only in subjects <7 years at baseline
PUL	X	X		X	X	X	X	X	X	Performed only in subjects ≥7 years at baseline
6-minute walk test (1 st test)	X	X		X	X	X	X	X	X	
6-minute walk test (2 nd test)			X						X	
NSAA	X	X		X	X	X	X	X	X	
Timed function tests	X	X		X	X	X	X	X	X	
Study drug dispensed			X	X	X	X	X	X	X	Open-label study drug dispensed at Visit 8
Study drug compliance			X	X	X	X	X	X	X	
12-lead ECG	X			X		X		X		
Spirometry	X	X						X		Required at all visits after subject loses ambulation
Echocardiogram	X							X		
Randomization		X								Access IRT system to randomize subject
Upper leg imaging		X		X		X		X		Performed only at pre-qualified sites. May be done between Visits 1 and 2 (pre-treatment assessment) or ±4 weeks of visit (post-treatment assessments).

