11.1.8 Magnetic Resonance Imaging

Progressive fatty and fibrotic replacement of muscle due to an absence of dystrophin underlies the phenotypic manifestations of muscle weakness in boys with DMD. Quantitative MRI enables non-invasive, objective measurement of muscle pathophysiology in patients with DMD [Willcocks 2016]. 3-point Dixon imaging separates muscle fat and water based on phase difference (chemical shift) and provides measurement of muscle fat without any confounding effect of muscle edema. A standardized MRI protocol has been developed to facilitate image acquisition across multiple sites. Using centralized data analysis, quantitative evaluations of muscle fat fraction can be derived for leg muscles with important functional roles, such as the vastus lateralis. Inclusion of MRI in this trial offers the potential for tying an imaging biomarker to clinical benefit. Due to the need for specific equipment and trained operators, MRI will be conducted only at sites that have been qualified to perform this assessment based on access to the necessary equipment and trained operators. Although only a subset of sites will participate, it has been reported in the literature that the sensitivity of MRI may reduce the sample size needed to demonstrate a treatment effect, compared to functional outcome measures such as the 6MWT [Bonati 2015, Willcocks 2016]; this hypothesis remains to be confirmed. A limited number of MRI sites will also assess muscle fat fraction by MRS to explore the correlation between MRI and MRS.

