2.3.3. Exploratory Endpoints

Exploratory endpoints include:

- Changes from baseline to Week 72 in PUL total score and domain subscores (in subjects ≥ 7 years old at baseline)
- Change from baseline to Week 72 in DMD Upper Limb PROM total score and domain subscores (in subjects ≥ 7 years old at baseline)
- Risk of loss of DMD Upper Limb PROM items over 72 weeks (in subjects ≥ 7 years old at baseline)
- Change from baseline to Week 72 in myometry parameters (in subjects < 7 years old at baseline)
- Change from baseline to Week 72 in muscle fat fraction as assessed by MRI (at pre-qualified sites only)
- Changes from baseline to Week 72 in HRQL as assessed by EuroQoL 5-Dimension (EQ-5D)
- Change from baseline to Week 72 in FVC

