4.8. Study Analysis Visit

Study analysis visits during double-blind treatment period will be derived as listed in [Table 2](#) based on days from randomization date to the corresponding visit date. Study analysis visits will be used in all by-visit summaries for both efficacy and safety assessments.

Table 2: Study Analysis Visit

| Analysis Visit | Scheduled Visit Number (Study Day) | Analysis Window (Study Day) |
|----------------|------------------------------------|---|
| DB Week 12 | Visit 3 (85) | [43, 126] |
| DB Week 24 | Visit 4 (169) | [127, 210] |
| DB Week 36 | Visit 5 (253) | [211, 294] |
| DB Week 48 | Visit 6 (337) | [295, 378] |
| DB Week 60 | Visit 7 (421) | [379, 462] |
| DB Week 72 | Visit 8 (505) | Any double-blind visit occurred on or after Day 463 |

Abbreviations: DB, double-blind.

Study day is calculated as visit date - randomization date + 1.

All assessments will be assigned to a study analysis visit based on study days. For a given subject, if multiple assessments are within the same analysis window, the one closest to the scheduled study day will be used for that analysis visit. In case of equal number of days to the scheduled visit date, the later assessment will be used for that given analysis visit.

For 6MWD at the Week 72 Visit (Visit 8), the date corresponding to the maximum of Day 1 and Day 2 will be used for deriving the study analysis visit.

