6.3.3. Muscle Fat Fraction

Muscle fat fraction data obtained (proton density fat fraction and MRS fat fraction) from MRI will be summarized by treatment groups at each visit based on both the mITT and ITT populations. The muscle fat fraction will also be summarized for subjects with the following subgroups:

- Baseline 6MWD <300 meters
- Baseline 6MWD ≥ 300 meters and time to rise from supine <5 seconds at baseline, or baseline 6MWD ≥ 300 meters, time to rise from supine ≥ 5 seconds at baseline, and younger than 7 or older than 16 years old

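### The Week 72 leg scan may fall up to about 4 weeks into open-label ataluren with no rule for handling it, and muscle fat fraction has no between-arm, baseline-adjusted analysis of change

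*Protocol*

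**What the plan says.** **Timing.** Protocol Section 6.2.26 states that "post-baseline imaging may be performed ± 4 weeks of visit date". Table 3 repeats this for upper leg imaging, while the visits themselves have a window of 7 days either side. Table 3 also notes "Open-label study drug dispensed at Visit 8". Section 5.1.1 places open-label treatment from Week 73, and Section 5.2.1 has blinded treatment run "for 72 weeks followed by continuous daily administration of open-label ataluren for an additional 72 weeks". The available text does not require the Visit 8 scan to come before the first open-label dose.

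**Assignment to Week 72.** Double-blind SAP Section 4.8, Table 2, assigns to Week 72 "Any double-blind visit occurred on or after Day 463". Overall-period SAP Section 4.9, Table 1, assigns Days 463 to 546 to Week 72, whatever drug is being taken.

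**Analysis.** Double-blind SAP Section 2.3.3 lists the endpoint as "Change from baseline to Week 72 in muscle fat fraction as assessed by MRI". Section 6.3.3 says that the data obtained "from MRI will be summarized by treatment groups at each visit based on both the mITT and ITT populations", and it names no change score, model or confidence interval. Overall-period SAP Section 6.3.3 summarises change from baseline by visit in ITT, with no model. Section 3.3.3 of the changes-from-planned-analysis document adds subgroup summaries only.

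**The concern.** Two gaps affect the same endpoint.

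First, the double-blind contrast is ataluren versus placebo up to Week 72, yet the scan window runs past the point at which placebo boys start ataluren. A late scan from such a boy could be tabulated as placebo at Week 72. It could instead be judged not to belong to a double-blind visit and left missing, because double-blind SAP Section 4.7 does not impute in by-visit efficacy summaries. Two programmers could follow the SAP and produce different tables.

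Second, the protocol sets an objective of determining ataluren's effect on skeletal muscle integrity. Section 11.1.8 justifies imaging partly because "Inclusion of MRI in this trial offers the potential for tying an imaging biomarker to clinical benefit". A table of fat fraction by arm and visit gives no estimate of that effect, and it leaves differences between boys in disease stage unadjusted. What is at stake is whether the trial answers its own imaging objective.

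**Working it through.** **No stated figure to reproduce.** The plan's only sample-size figure (154 subjects) is for 6MWD slope. None is given for imaging.

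**How late a scan can be.** Visit 8 is scheduled for Day 505, within 7 days either side, and a scan may follow by up to 28 days.
- Visit on Day 498: latest scan 498 + 28 = Day 526.
- Visit on Day 505: latest scan 505 + 28 = Day 533.
- Visit on Day 512: latest scan 512 + 28 = Day 540.

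All three days are on or after Day 463 and inside the overall-period window of Days 463 to 546. For a visit on schedule, the latest scan is 504 + 28 = 532 days after baseline, and at most 28/532 = 5.3% of that time is on open-label drug.

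**What a late scan does to the contrast.** This depends on how the effect builds up, which the documents do not say. Two assumed shapes bracket it.
- *Linear*, d per week, both arms scanned at Week 76: the contrast is 76d − 4d = 72d. This equals the Week 72 contrast, so nothing is lost against the intended target. Against an uncrossed Week 76 contrast the shortfall is 4/76 = 5.3% if every scan is that late. Scaled to assumed late shares of 10%, 25% and 50%, it is 0.5%, 1.3% and 2.6%.
- *Immediate and complete* (an extreme assumption): the loss equals the late share, so 10%, 25% and 50%.

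**What baseline adjustment is worth.** Let rho be the correlation between baseline and Week 72 fat fraction, assumed because no document gives it, with equal variances at both times. Standard errors compare as follows:
- ANCOVA to raw Week 72 means: sqrt(1 − rho²)
- change score to raw Week 72 means: sqrt(2(1 − rho))
- ANCOVA to change score: sqrt((1 + rho)/2)

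| rho | ANCOVA / raw | change / raw | ANCOVA / change |
|---|---|---|---|
| 0.80 | 0.60 | 0.63 | 0.95 |
| 0.90 | 0.44 | 0.45 | 0.97 |
| 0.95 | 0.31 | 0.32 | 0.99 |

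Most of the gain comes from using change at all. Beyond that, the model's main contribution is an estimated arm difference with an interval, adjusted for chance imbalance at baseline.

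**How comparable endpoints are treated.** In the double-blind SAP, PUL and PROM (Section 6.3.1) and myometry (Section 6.3.2) are also exploratory, and each has an ANCOVA after multiple imputation. Section 4.3 promises baseline covariates for primary and secondary endpoints only. Section 4.1 lists default summaries without a confidence interval. The SAP does cut at the first open-label dose for concomitant medications (Section 5.7) and for treatment-emergent adverse events in boys who complete the double-blind period (Section 7.1). It has no such rule for imaging.

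**The case against.** A reader might infer that the Week 72 imaging comparison is contaminated. The documents do not show that. The window is two-sided, only late scans are affected, their share is not given, and exposure is at most about 4 weeks. Under linear accrual the Week 72 contrast is unchanged. If only placebo boys were scanned late, further progression could even widen the gap between arms. If a double-blind visit is taken to end the day before the first open-label dose, as Section 5.7 defines the period for concomitant medications, late scans would be dropped and would contaminate nothing. This reduces the timing point to a possible effect and an unstated rule, but the rule is still missing.

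A reader might also take 0.60 to 0.31 as the precision that the plan gives up. That compares ANCOVA with raw Week 72 means. The overall-period SAP already tabulates change from baseline through Week 72, with a 95% CI on each mean (Section 4.2), and against that the gain is about 1 to 5%. This objection stands. It does not supply a between-arm estimate, and that table is limited to ITT and lies outside the double-blind SAP.

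Descriptive reporting of an exploratory, site-limited measure is legitimate, and FVC and HRQL are treated the same way. Boys at the imaging sites are still randomised, with baseline 6MWD and time to stand as stratification factors, so any imbalance is due to chance. Both points lower the priority. Finally, the section numbering of protocol Section 9.4 has gaps in the available text, so the lack of a model can be asserted for the SAPs and the changes document, not for the whole protocol.

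**Conclusion.** The point holds as a gap in specification. A scan assigned to Week 72 may be taken with up to about 4 weeks of open-label ataluren in a former-placebo boy (5.3% of the baseline-to-scan interval), and neither SAP says how it is handled. The double-blind SAP does not name the change from baseline that defines the endpoint. Neither SAP nor the changes document gives a between-arm estimate, a confidence interval for the difference, or a baseline-adjusted comparison of fat fraction.

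The effect on the imaging result cannot be sized from the documents. It runs from nothing, if the effect accrues linearly, to the late share itself, if the effect is immediate and complete. The precision figures rest on assumed correlations and equal variances. The endpoint is exploratory and outside the fixed testing sequence, so the primary and key secondary conclusions do not change.

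**What to change.** In double-blind SAP Section 6.3.3:
- Estimate the arm difference in change from baseline to Week 72, with a 95% CI, by ANCOVA with baseline fat fraction and the randomisation stratification factors. Label it exploratory and run it separately for MRI and MRS fat fraction. In mITT the time-to-stand factor drops out, because every boy there is at 5 seconds or more.
- Exclude from the Week 72 comparison any scan dated after the first open-label dose, in both arms so that scan timing stays comparable. Add a sensitivity analysis that includes these scans.
- Report how many scans were late, by arm, and their dates relative to that dose.

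Where scans are still to be scheduled, require in protocol Section 6.2.26 and Table 3 that the Visit 8 scan precede the first open-label dose. The overall-period SAP (Section 1) records that the double-blind data were locked on 11 April 2022. The scheduling change therefore comes too late for scans already taken, and the model should be reported as added after lock.

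The cost is one exploratory model, a narrower scan window at one visit, and possibly some Week 72 scans lost. No new procedure or data item is needed, since the overall-period SAP already relies on the date of first ataluren dose.
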